4.0 Eligibility

4.1 Inclusion Criteria

- Males and females willing to provide informed consent
- 18-35 or 55-75 years of age
- Non-smoker
- No antioxidant/vitamin supplementation
- No use of anti-inflammatory medication within last 2 weeks
- Aerobically trained (defined as performing aerobic exercise on ≥ 4 days/week, for ≥ 30 minutes, for at least the past 3 months AND a $\text{VO2max} \geq 75^{\text{th}}$ age- and sex-specific percentile according to ACSM)

OR

Sedentary (defined as being involved in less than 30 minutes of moderately-intense physical activity per day, < 3 days/week AND a $\text{VO2max} \leq 50^{\text{th}}$ age- and sex-specific percentile according to ACSM)

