4.2 Exclusion Criteria

- Body mass index $>35 \text{ kg/m}^2$
- Pregnancy, hormone replacement therapy, or peri-menopausal
- Known cardiovascular (i.e. atherosclerosis, uncontrolled hypertension, stroke, myocardial infarction, etc.), inflammatory (i.e. Crohn's disease, arthritis, etc.), or metabolic (i.e. Diabetes mellitus) disease
- Current use of >2 blood pressure medications, change in vasoactive medication type or dose within past 2 months.
- Regular use of medications to reduce inflammation (NSAIDS, aspirin, steroids, etc)
- Bleeding disorders
- Illness, other vaccination, or antioxidant use within 2 weeks prior to screening
- Typhoid vaccination within previous 2 years or prior adverse reaction
- VO2max in $51^{\text{st}} - 74^{\text{th}}$ age- and sex-specific percentile according to ACSM
- Non-English speaking participants

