6.0 Study Design and Procedures

Study site

All study procedures except the vaccination will be conducted in the Integrative Physiology Laboratory at the University of Illinois at Chicago located at [name] in the Disability, Health and Social Policy building (DHSP). The typhoid vaccination will be administered by a registered nurse at the Clinical Research Center at UIC.

Design

A comparative, observational study design will be conducted with a group of 15 low fit young adults, 15 low fit older adults, and 15 high fit older adults, for a total of 45 research participants.

Subjects will participate in three study visits, with at least 72 hours between the first two visits, and exactly 24 hours between the last two visits. Menstruating females will be studied during the first 7 days of menses, or during the placebo phase if taking oral contraceptives. Participants will arrive to each visit having refrained from exercise, alcohol, and caffeine for 24h prior to each test day. Participants will be tested in the post-prandial (no food, only water) state (>10 hours) for all visits. (Figure 1)

[figure not shown]

Figure 1. Study protocol schematic

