Visit 1. Following informed consent, participants will complete a health history, food recall, and physical activity questionnaire and undergo anthropometric (height, weight, waist and hip circumference) and body composition measures (DEXA scan). For women of childbearing age, the first visit will include a urine pregnancy test using a test stick. Baseline influence of oxidative stress on endothelial and microvascular function will be assessed following supine rest and resting hemodynamics. Measures will include: 1) endothelial function, 2) microvascular function, 3) arterial stiffness, and 4) circulating markers of oxidative stress. Participants will then orally ingest 2g of ascorbic acid. This dose produces a physiological level of ascorbate in plasma[35], has been used in previous studies to improve endothelial function[35–39], and reaches optimal absorption after 2 hours[40,41]. During this time, an assessment of general cognitive function will be completed using the Montreal Cognitive Assessment (MOCA) and Symbol Digits Modality Test (SDMT), and be familiarized with a working memory cognitive function task (NBACK) by completing the task four times throughout the two hour period. Following 2 hours, all measures will be repeated to determine the influence of the antioxidant. The visit will finish with a treadmill exercise test to evaluate cardiorespiratory fitness (VO₂peak).

Visit 2. At least 72 hours later, participants will arrive after an overnight fast (>8 h) and undergo supine baseline measures of: 1) endothelial function, 2) microvascular function, 3) arterial stiffness, 4) cerebrovascular function and 5) cognitive function, 6) heart function and 7) circulating markers of inflammation

and oxidative stress. The typhoid vaccination (Typhuim Vi, Sanofi Pasteur SA) will then be administered by a registered nurse. Acute inflammation is often induced in cardiovascular research by use of either the influenza or typhoid vaccination [10,11,13,23,33,34,42]. Vaccinations provide a safe and controlled inflammatory response, in which the typhoid vaccination has shown to increase hsCRP up to at least 32 hours post-vaccination[13].

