Visit 3. Exactly 24-hours following Visit 2, participants will return to the lab under the same conditions. Visit 2 will be repeated. Following baseline measures, participants will consume 2g of ascorbic acid, as completed in Visit 1. Following 2 hours, measures of 1) endothelial function, 2) microvascular function, 3) arterial stiffness and 4) circulating markers of oxidative stress.will be repeated to determine the influence of the antioxidant.

All procedures are being completed for research purposes. The table below shows the estimated time commitment for each study visit and procedure.

	Visit 1	Visit 2	Visit 3
Informed Consent/ Questionnaires	30		
Anthropometrics	5		
DEXA	10		
Blood Draw	10	10	10
Rest/Preparation	10	10	10
Vascular Assessment			
Blood pressure	7	7	7
FMD/NIRS	13	13	13
Arterial stiffness (PWV)	10	10	10
Brain blood flow (TCD)		15	15
Carotid Flow		5	5
Heart Function		15	15
Cognitive: NBACK		12	
Vaccination		15	
Vit C	120		120
			Cognitive:
			NBACK
			MOCA
			SDMT
Blood Draw	10		10
Vascular Assessment			
Blood pressure	7		7
FMD/NIRS	13		13

Arterial stiffness (PWV)	10	10
Maximal Exercise Test	30	
TOTAL TIME (minutes)	285	112
Hours:	4.75	1.87
		245
		4.08

Measurements

DEXA Scan

We will determine percent body fat via a whole body scan by dual energy x-ray absorptiometry (GE, IDXA, Madison, Wi), which will be operated and calibrated using the manufacturer's stated guidelines. The duration of the scan will be less than 10 min and the subject will be exposed to a radiation dose of ≤ 0.3 mrem based upon the manufacturer's specifications and calculations from Standford Dosimetry, LLC RADAR Medical Procedure Radiation Dose Calculator. This amount of research protocol radiation exposure is minimal given the estimated effective equivalent dose is below the 100 mrem per year, a limit set by the Nuclear Regulatory Commission for "general public" exposure.

Venous blood samples

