Studies involving use of product

Participants will receive a Typhoid Vi Polysaccharide Vaccine (Typhim Vi, Sanofi Pasteur SA). It will be administered intramuscularly at the deltoid (upper arm) of the non-dominant arm in a dose of 0.5 mL by a registered nurse. The product will be purchased from the manufacturer through UIC Investigational Pharmacy. The vaccination will be stored at 35° to 46° F in a temperature controlled refrigerator

in the Integrative Physiology Lab in the DHSP Building in a locked room in a controlled access suite. On-study personnel will have access. A log will be kept with date and subject number for each dose of the vaccine used. Adverse events will be immediately reported to the principal investigator, who will complete an Adverse Event Report Form. If it is deemed a severe adverse event, it will be reported to the IRB within 24 to 48 hours. Based on data from clinical trials with over 4,000 subjects, adverse reactions may consist of: local tenderness, pain, induration or erythema at the injection site; or, a systemic response of malaise, headache, myalgia, nausea, diarrhea, feverish, or vomiting. No severe or unusual side effects were observed and most adverse experiences were generally limited to 48 hours.

Participants will also receive 2g Vitamin C on the first and third visit. It will be administered orally. Supplementation will be ingested in front of laboratory personnel. This supplementation does not exceed daily recommendation and has been previously shown to acutely improve endothelial function[35–39]. The product will be purchased and stored in the IPL in the DHSP Building. On-study personnel will have access. A log will be kept with the date and subject number for each dose given. Adverse events will be immediately reported to the principal investigator, who will complete an Adverse Event Report Form. If it is deemed a severe adverse event, it will be reported to the IRB within 24 to 48 hours. There are no known risks associated with the administration of Vitamin C. The dosage of antioxidant vitamins are the same as those sold over the counter and safe. No side effects have been reported with this dose.

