7.0 Expected Risks/Benefits

1. **Typhoid vaccine:** Mild reactions to the typhoid vaccine may occur, such as fever, headache, redness/swelling at the site of injection, nausea, or muscle pain. You may also faint or an allergic reaction may occur. The risk of serious harm or death is extremely small and serious problems from the typhoid vaccine are very rare. Participants with a history of adverse reactions to the typhoid vaccine, will be removed from the study.
2. **Health information:** Risk of loss of privacy or confidentiality of health information. To minimize the risk, all data will be stored coded.
3. **Questionnaires:** Participants may feel uncomfortable providing personal information in the questionnaires.
4. **Blood pressure:** Blood pressure will be measured using a cuff around the arm. Subjects may feel some discomfort when the cuff is inflated on the arm or may feel some tingling in the fingers.
5. **ECG (Heart rate):** Skin redness may appear where the electrodes are placed on the skin for the ECG.
6. **Pulse wave analysis and Pulse wave velocity:** No known risks.
7. **Ultrasound:** No known risks. All efforts will be made to maintain patient's modesty. The gel used during the ultrasound may feel cool and sticky and is hypoallergenic (not likely to cause an allergic reaction) and washes off easily.

8. **Fasting:** May cause mild discomfort and hunger pains. If participants develop any further symptoms due to fasting, we have snacks and drinks (water and juice) available. Participants will *not* have to perform the treadmill test in the fasted state, reducing risk.
9. **Flow-mediated dilation:** Subjects may feel uncomfortable (i.e. the arm may “fall asleep”) when the blood pressure cuff is inflated for 5 minutes during flow-mediated dilation but this will subside when the cuff is released.

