13.3 Unanticipated Problems

When an unanticipated problem is identified, the staff member identifying the adverse event will immediately report it to the principal investigator. The principal investigator will then contact the participant and an Adverse Event Report Form will be completed. If the principal investigator feels that a serious adverse event has occurred, a report of the serious adverse event will be forwarded to the UIC IRB within 24-48 hours of occurrence. If the event is not classified as a serious adverse event, it will be reported to the UIC IRB upon the next renewal.

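### Anti-inflammatory drugs are restricted at entry, but the visible protocol neither names them in the visit rules nor records their use between vaccination and Visit 3

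*Combined protocol and SAP*

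**What the plan says.** Two entry criteria deal with anti-inflammatory drugs. Section 4.1 requires "No use of anti-inflammatory medication within last 2 weeks". Section 4.2 excludes "Regular use of medications to reduce inflammation (NSAIDS, aspirin, steroids, etc".

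The rule repeated for every visit is in Section 6.0 (Design): "Participants will arrive to each visit having refrained from exercise, alcohol, and caffeine for 24h prior to each test day". Fasting is required as well. No drug is named.

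History and questionnaires belong to Visit 1: "Following informed consent, participants will complete a health history, food recall, and physical activity questionnaire". The timetable in Section 6.0 gives questionnaire time to Visit 1 only. For Visit 3 the text says that "participants will return to the lab under the same conditions. Visit 2 will be repeated". Visit 2 as described contains no medication question.

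The vaccine is given at Visit 2, and Visit 3 follows exactly 24 hours later. Section 6.0 (use of product) lists local pain and "a systemic response of malaise, headache, myalgia, nausea, diarrhea, feverish, or vomiting" as possible reactions, mostly confined to 48 hours. Section 7.0 adds: "Mild reactions to the typhoid vaccine may occur, such as fever, headache".

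The product logs cover vaccine and vitamin C doses. For adverse events, Section 13.3 says: "The principal investigator will then contact the participant and an Adverse Event Report Form will be completed". Section 12.0 has no rule for participants who took an anti-inflammatory drug after vaccination.

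**The concern.** The protocol treats anti-inflammatory drugs as a threat at entry. It then appears to leave them unaddressed in the 24 hours when they matter most. Vaccination is the study's only inflammatory stimulus, and the listed reactions are ones for which people may take an over-the-counter drug.

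Section 2.0 gives the reason to care. It reports that salsalate lowers oxidative stress and improves endothelial function, and that the improvement was seen in older sedentary adults but not in trained or younger ones. Two inferences are exposed:

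- **Aim 1** compares the change from Visit 2 to Visit 3 baseline across groups. Section 12.0 expects FMD to fall in young and high fit older adults. A drug could blunt that fall, or raise FMD in low fit older adults.
- **Aim 2** starts from the Visit 3 value before vitamin C. If a drug has already prevented part of the dysfunction, vitamin C has less to reverse. Section 12.0 would read an absent effect as evidence for a mechanism other than oxidative stress.

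Use that is not recorded at Visit 3 cannot be reliably recovered later.

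**Working it through.** **Text check.** The question is whether any visible section restricts or records these drugs after entry.

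| Place | Restricts use after vaccination? | Records use after vaccination? |
|---|---|---|
| 4.1 and 4.2, eligibility | Not clearly; entry criteria | No |
| 6.0, pre-visit rule | No drug named | No |
| 6.0, Visit 1 history and questionnaires | No | No; taken before vaccination |
| 6.0, Visit 3 | Only if sameness of conditions is read to include drugs | No |
| 6.0, product logs | No | Vaccine and vitamin C doses only |
| 13.3, adverse event form | No | Depends on an event being identified; drug use not mentioned |
| 12.0, analysis | No | No |

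**Illustration of size.** The plan has no figure to reproduce. The documents give no symptom rate, no usage rate and no effect of an over-the-counter dose. Only n = 15 per group comes from the documents (Section 6.0, Design). Everything else is assumed:

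- D = the true FMD fall in high fit older adults from Visit 2 to Visit 3; the true change in low fit older adults is 0.
- uH, uL = number of drug users in the high fit and low fit older groups, 0 to 3 each.
- b = fraction of the fall that the drug blunts in a high fit user; r = rise in a low fit user as a fraction of D. Each runs from 0.25 to 1.

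*Step 1, each group's own change.*
High fit: −D × (1 − uH × b/15). With uH = 1, b = 0.25 this is −0.983 D; with uH = 3, b = 1 it is −0.80 D.
Low fit: +D × uL × r/15. With uL = 3, r = 1 it is +0.20 D.
Both move the same way, toward less decline.

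*Step 2, the contrast between older groups* (low fit change minus high fit change; true value D).
Contrast = D × [1 + (uL × r − uH × b)/15].

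| uH | b | uL | r | Shift in contrast |
|---|---|---|---|---|
| 1 | 0.25 | 0 | – | −0.25/15 = −1.7% |
| 2 | 0.5 | 0 | – | −1.0/15 = −6.7% |
| 3 | 1 | 0 | – | −3.0/15 = −20.0% |
| 0 | – | 1 | 0.25 | +0.25/15 = +1.7% |
| 0 | – | 2 | 0.5 | +1.0/15 = +6.7% |
| 0 | – | 3 | 1 | +3.0/15 = +20.0% |
| 3 | 0.5 | 1 | 0.5 | (0.5 − 1.5)/15 = −6.7% |
| 1 | 0.5 | 3 | 0.5 | (1.5 − 0.5)/15 = +6.7% |
| 2 | 0.5 | 2 | 0.5 | 0% |
| 3 | 0.25 | 3 | 0.5 | (1.5 − 0.75)/15 = +5.0% |

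The sign depends on which group uses more and responds more. Equal use and equal effect cancel.

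*Step 3, Aim 2.* The dysfunction left for vitamin C to reverse in the high fit group is D × (1 − uH × b/15). At the extreme, uH = 3 and b = 1, it is 0.80 D.

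*Step 4, chance of any use.* If each participant has an assumed probability p of taking a drug, the chance of at least one user in a group of 15 is 1 − (1 − p)^15. This gives 54% for p = 5%, 79% for p = 10% and 96% for p = 20%.

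**The case against.** **The restriction may exist.** The consent text, the packet sent before Visit 1 and the study schematic are not shown, and any of them could carry an instruction. The two-week criterion in Section 4.1 has no anchor date, and the sameness of conditions at Visit 3 could be read to extend it. This stands as a limit: a reader might infer that participants are never told to avoid these drugs, and the documents do not establish that. But the neighbouring two-week rule in Section 4.2 is tied to screening, and even if the ban continues, no visible section checks it.

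**A blunted response would leave traces.** CRP and IL-6 are measured at all time points (Section 6.0, Venous blood samples). Section 12.0 also plans an analysis of Visit 2 baseline, Visit 3 before vitamin C and Visit 3 after it. A prevented fall would look different there from a fall that vitamin C fails to correct. This largely stands. These data could partly reveal a blunted response, but they cannot show that a drug caused it.

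**The mechanism is thin.** The only drug evidence is the cited salsalate work, given without dose or duration and not obtained during vaccine-induced inflammation. It reports no improvement in trained or younger adults. Nothing visible shows that an occasional dose blunts the fall in those groups. This stands, and it is why the size cannot be stated.

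**Two stronger readings are not supported.** A reader might infer that drug use could push a group's own change from Visit 2 to Visit 3 in either direction. Both mechanisms available from the documents move it toward less decline, and nothing visible shows such a drug lowering FMD. A reader might also infer that unrecorded use would account for a null vitamin C result. In the working's most extreme case 80% of the dysfunction remains, and the three-time-point analysis limits that explanation further.

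**The study is exploratory.** Section 9.0 says so. That lowers the stakes, but the same section intends the data for planning later studies, so a distorted effect could carry forward.

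**Conclusion.** The gap holds for the visible protocol: drugs restricted at entry are not named in the visit rules, and their use between vaccination and Visit 3 is not recorded. Such use could blunt a group's own decline. It could bias the Aim 1 contrast in either direction only if use or response differs between groups. For Aim 2 it could leave less dysfunction to reverse, with partial detection from measurements already planned.

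The size is unknown and may be negligible. The range of −20% to +20% of the older-group contrast rests on assumed user counts, assumed drug effects and an assumed zero change in low fit older adults. Its ends need 3 of 15 users in one group, none in the other, and a full effect. Severity is minor; the case for acting is that the information is cheap to collect and cannot be reliably recovered afterwards.

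**What to change.** 1. **Section 6.0, Design.** Add non-prescribed NSAIDs, aspirin and other anti-inflammatory drugs to the 24-hour restrictions for Visits 2 and 3, with the second period running from vaccination to the end of Visit 3. Participants who need symptom relief remain free to take a drug and are asked to report it.
2. **Section 6.0, Visits 2 and 3.** On arrival, ask about and record any anti-inflammatory or analgesic taken, with dose and time. Visit 2 is included because it is the reference for the same contrast.
3. **Section 12.0.** Keep all participants in the main analysis, report use by group, and treat any analysis without users as supportive only. Removing users may remove the strongest reactors, possibly unequally by group.

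The cost is a mild restriction on participants, one extra question at each of two visits, and a line of reporting. Because symptom relief is still allowed, the record is the main safeguard.

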4.2 Exclusion Criteria

- Body mass index $>35 \text{ kg/m}^2$
- Pregnancy, hormone replacement therapy, or peri-menopausal
- Known cardiovascular (i.e. atherosclerosis, uncontrolled hypertension, stroke, myocardial infarction, etc.), inflammatory (i.e. Crohn's disease, arthritis, etc.), or metabolic (i.e. Diabetes mellitus) disease
- Current use of >2 blood pressure medications, change in vasoactive medication type or dose within past 2 months.
- Regular use of medications to reduce inflammation (NSAIDS, aspirin, steroids, etc)
- Bleeding disorders
- Illness, other vaccination, or antioxidant use within 2 weeks prior to screening
- Typhoid vaccination within previous 2 years or prior adverse reaction
- VO2max in $51^{\text{st}} - 74^{\text{th}}$ age- and sex-specific percentile according to ACSM
- Non-English speaking participants

4.3 Excluded or Vulnerable Populations

- Pregnant women, women on hormone replacement therapy, and peri-menopausal women will be excluded due to the changes in hormonal concentrations, hemodynamics, and altered exercise capacity
- In addition, we exclude non-English speakers as the researchers must ensure the subjects completely understand the purposes and risks associated with our study and we do not have any Spanish speaking research personnel.

5.0 Subject Enrollment

Subjects will be recruited from the UIC campus and Chicago community using an IRB approved recruitment flyer, internet recruitment ad (i.e. UIC website, Craig's List, ResearchMatch, etc.), social media (i.e. Facebook, Twitter, etc.) and word of mouth including speaking engagements. Subjects will be asked to contact the IPL for further information about the study and subsequent screening for eligibility by either phone or e-mailing [name].

After the screening is complete, participants will be asked if they are still interested in the study. If interested, their age, gender, and group (sedentary or active) will be kept by [name]. Once an individual of the same gender, similar age (within 2 years) and opposite group has been identified, participants will be contacted again for scheduling of visits. We have not had issues with this type of recruitment in the past.

If still interested, a packet will be sent (mail or email) to the potential subject with a copy of the informed consent and information regarding the first laboratory visit. All subjects will sign an institutionally approved informed consent prior to participation in the study during visit one.

6.0 Study Design and Procedures

Study site

All study procedures except the vaccination will be conducted in the Integrative Physiology Laboratory at the University of Illinois at Chicago located at [name] in the Disability, Health and Social Policy building (DHSP). The typhoid vaccination will be administered by a registered nurse at the Clinical Research Center at UIC.

Design

A comparative, observational study design will be conducted with a group of 15 low fit young adults, 15 low fit older adults, and 15 high fit older adults, for a total of 45 research participants.

Subjects will participate in three study visits, with at least 72 hours between the first two visits, and exactly 24 hours between the last two visits. Menstruating females will be studied during the first 7 days of menses, or during the placebo phase if taking oral contraceptives. Participants will arrive to each visit having refrained from exercise, alcohol, and caffeine for 24h prior to each test day. Participants will be tested in the post-prandial (no food, only water) state (>10 hours) for all visits. (Figure 1)

[figure not shown]

Figure 1. Study protocol schematic

Visit 1. Following informed consent, participants will complete a health history, food recall, and physical activity questionnaire and undergo anthropometric (height, weight, waist and hip circumference) and body composition measures (DEXA scan). For women of childbearing age, the first visit will include a urine pregnancy test using a test stick. Baseline influence of oxidative stress on endothelial and microvascular function will be assessed following supine rest and resting hemodynamics. Measures will include: 1) endothelial function, 2) microvascular function, 3) arterial stiffness, and 4) circulating markers of oxidative stress. Participants will then orally ingest 2g of ascorbic acid. This dose produces a physiological level of ascorbate in plasma[35], has been used in previous studies to improve endothelial function[35–39], and reaches optimal absorption after 2 hours[40,41]. During this time, an assessment of general cognitive function will be completed using the Montreal Cognitive Assessment (MOCA) and Symbol Digits Modality Test (SDMT), and be familiarized with a working memory cognitive function task (NBACK) by completing the task four times throughout the two hour period. Following 2 hours, all measures will be repeated to determine the influence of the antioxidant. The visit will finish with a treadmill exercise test to evaluate cardiorespiratory fitness (VO₂peak).

Visit 2. At least 72 hours later, participants will arrive after an overnight fast (>8 h) and undergo supine baseline measures of: 1) endothelial function, 2) microvascular function, 3) arterial stiffness, 4) cerebrovascular function and 5) cognitive function, 6) heart function and 7) circulating markers of inflammation

and oxidative stress. The typhoid vaccination (Typhuim Vi, Sanofi Pasteur SA) will then be administered by a registered nurse. Acute inflammation is often induced in cardiovascular research by use of either the influenza or typhoid vaccination [10,11,13,23,33,34,42]. Vaccinations provide a safe and controlled inflammatory response, in which the typhoid vaccination has shown to increase hsCRP up to at least 32 hours post-vaccination[13].

Visit 3. Exactly 24-hours following Visit 2, participants will return to the lab under the same conditions. Visit 2 will be repeated. Following baseline measures, participants will consume 2g of ascorbic acid, as completed in Visit 1. Following 2 hours, measures of 1) endothelial function, 2) microvascular function, 3) arterial stiffness and 4) circulating markers of oxidative stress.will be repeated to determine the influence of the antioxidant.

All procedures are being completed for research purposes. The table below shows the estimated time commitment for each study visit and procedure.

	Visit 1	Visit 2	Visit 3
Informed Consent/ Questionnaires	30		
Anthropometrics	5		
DEXA	10		
Blood Draw	10	10	10
Rest/Preparation	10	10	10
Vascular Assessment			
Blood pressure	7	7	7
FMD/NIRS	13	13	13
Arterial stiffness (PWV)	10	10	10
Brain blood flow (TCD)		15	15
Carotid Flow		5	5
Heart Function		15	15
Cognitive: NBACK		12	
Vaccination		15	
Vit C	120		120
			Cognitive:
			NBACK
			MOCA
			SDMT
Blood Draw	10		10
Vascular Assessment			
Blood pressure	7		7
FMD/NIRS	13		13

Arterial stiffness (PWV)	10	10
Maximal Exercise Test	30	
TOTAL TIME (minutes)	285	112
Hours:	4.75	1.87
		245
		4.08

Measurements

DEXA Scan

We will determine percent body fat via a whole body scan by dual energy x-ray absorptiometry (GE, IDXA, Madison, Wi), which will be operated and calibrated using the manufacturer's stated guidelines. The duration of the scan will be less than 10 min and the subject will be exposed to a radiation dose of ≤ 0.3 mrem based upon the manufacturer's specifications and calculations from Standford Dosimetry, LLC RADAR Medical Procedure Radiation Dose Calculator. This amount of research protocol radiation exposure is minimal given the estimated effective equivalent dose is below the 100 mrem per year, a limit set by the Nuclear Regulatory Commission for "general public" exposure.

Venous blood samples

A blood sample will be collected at baseline during each visit (3 times) and following Vit C consumption (2 times). During the first visit, each blood sample will be 15 mL (approximately 1 tbsp). On visit 2 and 3, the baseline blood draw will be 25 mL (approximately 5 tsp). The final blood draw on visit 3 will be 15 mL (approximately 1 tbsp). At all time points, we will measure C-reactive protein and interleukin-6 for inflammatory markers, oxidized LDL as a marker of oxidative stress, total antioxidant capacity and ascorbate for antioxidant capacity, and endothelial extracellular vesicles, in which additional analyses on inflammatory markers may be performed. The baseline blood draw of visit 2 and 3 will also assess the cholesterol panel (Total cholesterol, HDL cholesterol, non-HDL cholesterol, triglycerides, LDL cholesterol, TC/HDL ratio) and glucose. The additional 10 mL during the baseline blood draw on visit 2 and 3 will be used for analyses of peripheral blood mononuclear cells, which provide valuable information about immune function. Immediately after acquisition of venous blood, plasma or serum will be separated by centrifugation (3000g at 4°C for 15 minutes), placed in aliquots, and stored at -80°C.

Blood pressure

Blood pressure will be measured in the arm using an automated microprocessor controlled ambulatory blood pressure monitor (Mobil-O-Graph 24 PWA, I.E.M, Stolberg Germany) in the supine position according to the guidelines of the American Heart Association. BP will be measured twice, one minute apart, and the average of the two values will use as resting BP. If the two BP measurements

differ by more than 5 mmHg, a third measurement will be taken. Cardiovascular variables such as derived ascending aortic BP waveform and central arterial indices (PWV and pulse wave analysis), stroke volume and cardiac output can be calculated from the pressure waveforms.

For central blood pressure, radial artery pressure waveforms will be attained in the supine position from a 10-second epoch using applanation tonometry and a high-fidelity strain gauge transducer (Millar Instruments, Houston, TX) [43]. A central aortic pressure waveform is reconstructed from the aforementioned radial artery pressure waveform using a generalized validated transfer function (SphygmoCor, AtCor Medical, Sydney, Australia). From this reconstructed waveform, aortic pressures, end-systolic pressure, and sub-endocardial viability index (a ratio of diastolic to systolic pressure-time intervals) will be obtained [43]. Only recordings receiving an in-device quality index $\geq 80\%$ will be included in analysis [43]. This index is derived from a weighted algorithm that examines average pulse height (average height of the pulse waveforms measured), pulse height variation (amount of variation in the height of the pulse waveforms measured), and the diastolic variation (an index of baseline pressure consistency during the measurement attained from the variation in the diastolic inflection point of the pulse waveform). Previous work shows that reproducibility of measures attained from this technique is high [44].

Pulse wave velocity (PWV)

Approximately 20-sec of pressure waveforms will be collected at the brachial, common carotid, and femoral arteries using a high-fidelity strain-gauge transducer. PWV will be calculated from the distances between measurement points and the measured time delay between proximal (carotid) and distal (femoral) waveforms (NIHem, Cardiovascular Engineering Inc.). The brachial waveforms will not be used for PWV calculations, but are necessary for calibrating carotid blood pressure (described below).

Carotid Blood Pressure

Carotid artery pressure waveforms obtained during the measurement of PWV will be ensemble averaged to construct a carotid pressure waveform. This carotid waveform is then calibrated to brachial waveforms and brachial mean and diastolic pressure. The resulting carotid systolic pressure is necessary for calibrating carotid stiffness measures (described below).

Flow-Mediated Dilation (FMD)

Brachial artery vasodilator function will be noninvasively measured through assessment of brachial artery dilatation using ultrasonography (Hitachi Aloka, Alpha 7 Japan). The brachial artery will be imaged in longitudinal section, 5–10 cm proximal to placement of a blood pressure cuff, just below the antecubital fossa, using a high frequency (5–13 MHz) linear array probe. Endothelium-

dependent, flow-mediated dilatation (FMD) of the brachial artery will be measured at baseline and again for 5 minutes following ischemic stimulus (inflation of a blood pressure cuff around the forearm to 250 mmHg for 5 minutes). After cuff deflation, resultant reactive hyperemia is calculated as the flow change from baseline and expressed as a percentage change in blood flow [45]. Analysis of the FMD will be carried out using a semi-automated edge detection software system. This system requires an ECG and will be measured by placing 3 electrodes on the torso of the subject. Arterial diameter response will be calculated as percentage change in brachial artery diameter from baseline and controlled for the shear stimulus created by the hyperemic flow. The computerized image analysis system with edge-detection software significantly attenuates observer error over manual methods and allows the detection of changes in endothelial function with substantially fewer subjects. This method conforms to the guidelines set out for the ultrasound measurement of endothelium-dependent FMD of the brachial artery [45].

Near-Infrared Spectroscopy (NIRS)

Tissue oxygenation saturation will be measured non-invasively by near-infrared spectroscopy (OxiplexTS, ISS Inc., Champaign, IL) on the forearm during the flow mediated dilation. The small NIRS sensor will be held in place with a flexible elastic band.

Transcranial Doppler

Cerebral blood flow velocity will be measured for 7 minutes in a resting state in the middle cerebral artery (MCA) using two 2-MHz transcranial Doppler ultrasound probe (TOCM Neurovision, MultiGon Industries, INC. Elmsford NY) fitted with a specific cushioned headpiece to hold the probe in place. The Doppler probe will be placed at the temporal window on the side of the head to insonate the vessels. The blood velocity wave form will be recorded continuously at 500 Hz and stored off-line for subsequent analysis of the systolic, diastolic and mean blood flow velocities. Brain blood velocity is influenced by carbon dioxide, thus, we will monitor end tidal CO₂ throughout this testing period. A 5-minute average at the end of the 7 minute period will be used for analyses.

Carotid Ultrasonography

Carotid stiffness:

Carotid stiffness is a common clinical marker and independent risk factor for future vascular events. Carotid stiffness will be assessed using high fidelity ultrasound (Hitachi Aloka Alpha 7, Japan) and high frequency (7-13 MHz) linear probe. Carotid artery distension will be assessed using wall-tracking and simultaneous measurement of blood velocity. Stiffness measures are generally calculated by adjusting carotid artery compliance for changes in carotid blood pressure. Measures of carotid stiffness will include carotid B-stiffness, Elastic modulus, and PWV-B using the following equations:

$$\text{B-stiffness} = (\log P_1/P_0)/(D_1-D_0)/D_0;$$

$$\text{Elastic modulus} = (P_1/P_0)/((D_1-D_0)/D_0)$$

$$PWV-B = (\sqrt{((B\text{-stiffness}) \times P_1) / 2\rho}) / 2\rho$$

where P_1 and P_0 are the highest (systolic) and lowest (diastolic) carotid pressures and D_1 and D_0 are the maximum (systolic) and minimum (diastolic) diameters.

Carotid Blood Flow:

Carotid blood flow will be measured on the neck using the same ultrasound probe described for carotid stiffness. Carotid artery diameter and blood velocity will be measured with the probe placed on the skin over the carotid artery with 60 degree insonation angle. Common carotid blood flow will be assessed approximately 1-2 cm proximal to the carotid bifurcation. Internal carotid blood flow will be measured just distal to the carotid bifurcation to obtain measures of carotid blood flow that feed directly into the middle cerebral arteries.

Cognitive Function

Montreal Cognitive Assessment (MOCA):

The MOCA is a tool that can be used to systematically and thoroughly assess global cognitive status. It assesses different cognitive domains: attention and concentration, executive functions, memory, language, visuoconstructional skills, conceptual thinking, calculations, and orientation. The maximum score is 30, in which a score of 26 or greater is considered normal. The MOCA takes only 8-12 minutes to administer and is therefore practical to use repeatedly and routinely.

Symbol Digits Modality Test (SDMT):

The SDMT is a global test of cognitive impairment and is associated with selective attention and working memory. This test involves a visual substitution task, whereby the individual has 90 seconds to orally pair specific numbers with given geometric figures as quickly as possible. The test score is the number of correctly paired shapes/numbers.

N-back:

The N-back is a working memory task that lasts approximately 8 minutes.

Participants will be presented with a series of digits one at a time. They will be instructed to press the 'right' response button if the number presented to them matches the digit that was presented 2 numbers previously. Participants will be instructed to hit the 'left' response button for every digit presented to them that does not match the number 2 digits prior. This test is widely used in cognitive psychology as a measure working memory and has been used previously following acute perturbations.

Heart function (cardiac echocardiography)

Cardiac output (Q), stroke volume (SV), and end systolic volume (ESV) will be assessed at rest using two-dimensional echocardiography via a Hitachi Aloka Alpha 7 system (Tokyo, Japan). With subjects in the left lateral position, measurements will be obtained using the four-chamber apical view. The interior of the left ventricle will be traced manually during both end systole and end

